Summary of the Study Protocol

Title	Implementation and evaluation of a post-diagnostic announcement protocol at the Neuroretinal Disease Reference Center RefeRet, Quinze-Vingts Hospital.
Acronyme	RP-DIAG
Principal Investigator	Pr [name], CRMR
Sponsor	Quinze-Vingts National Vision Hospital (HNV des 15-20)
Study Justification	Retinitis pigmentosa (RP), the main genetic retinal dystrophy, affects approximately 1 in 4,000 people and is characterized by progressive vision loss. Receiving the diagnosis is often challenging: the long medical journey and lack of clear guidance increase anxiety, sometimes leading to a break in follow-up care. Unlike in oncology, there are no established post-diagnosis recommendations in this field. The current process at the Quinze-Vingts National Vision Hospital is limited to a consultation with the ophthalmologist, without formal coordination of psychological or nurse support. The RP-DIAG study aims to structure post-diagnosis follow-up (nurse and psychological support) and to evaluate its feasibility, impact, and potential for long-term implementation and adaptation in other rare disease centers.
Study Objectives	
 1. To evaluate a new post-diagnostic paramedical support pathway (nurse and psychological support) in order to improve care for patients with retinitis pigmentosa (RP). 2. To collect data on patients' psychological experience after diagnosis using the Hospital Anxiety and Depression Scale (HADS). 3. To assess the feasibility of generalizing the support pathway, including the workload for clinical teams, using the RETEX questionnaire, and to provide the basis for a standardized, sustainable post-diagnostic protocol that could potentially be reproduced in other ophthalmology rare disease centers.
Study Category and Type	Pilot study, RIPH2 category. Randomized, prospective, longitudinal, monocentric comparative study.
Evaluation Criteria and Outcome Measures	
 1. Patient-perceived satisfaction: Measured using the PREM (Patient-Reported Experience Measure) questionnaire, comparing: 
 – An experimental group receiving the structured nurse/psychological follow-up – A control group receiving usual care Measurement will be performed at 12 months. 2. Psychological impact: Change in HADS (Hospital Anxiety and Depression Scale) scores in the experimental group at 15 days, 6 months, and 12 months. 3. Paramedical team feedback: Collected via an observation log (RETEX questionnaire) to identify difficulties (organizational, logistical, interpersonal) and qualitatively and quantitatively evaluate the benefits of the intervention.
Inclusion Criteria	
 - Diagnosed with retinitis pigmentosa and receiving care at the Rare Disease Reference Center (CRMR), with diagnosis disclosure occurring after the project's initiation. - Aged between 18 and 65 years. - Male or female. - French-speaking. - Has a valid telephone number. - Resident of France.
Exclusion Criteria	
 - Individuals enrolled in a therapeutic clinical trial (for 12 months) - Individuals deprived of liberty by judicial or administrative decision (art. L1121-6 of the French Public Health Code) - Adults under legal protection measures or unable to provide consent (art. L1121-8 of the French Public Health Code) - Individuals with other medical conditions or taking treatments likely to interfere with study assessments - Participants unable to attend all study visits

Summary of the Study Protocol

	
- Pregnant, postpartum, or breastfeeding women (according to art. L1121-5 of the French Public Health Code).
																				
Criteria for early withdrawal or study discontinuation	
- Occurrence of other medical conditions or treatments which could interfere with the planned assessments of the study;
 
- A participant may decide at any time to withdraw from the study;
 
- A participant may also be withdrawn from the study by the investigator.
																				
Constraints and Risks	This pilot study does not present any foreseeable medical risks.																				
Population	
Target population: Adult patients diagnosed with retinitis pigmentosa (RP) who meet the inclusion criteria – first encounter with the name of their condition.
 
Sample: 80 patients (40 in the experimental group, 40 in the control group).
 
Randomization: Performed using the RedCAP software.
																				
Study Procedure	
Experimental Group (n=40)
 
 Visit 1 (Diagnosis Announcement): Ophthalmologist consultation; project information; optional initial discussion with the nurse. Consent Collection Visit 2 (Day 15): Nurse consultation (in-person or by phone, ~1 hour) to explain the disease and procedures, and assess emotional state (HADS-1). Visit 3 (6 months): Nurse consultation (HADS-2); psychologist consultation offered. Visit 4 (12 months): Ophthalmology consultation; nurse consultation (HADS-3); PREM questionnaire to assess patient satisfaction. 
Control Group (n=40)
 
 Usual care: Diagnosis consultation followed by a 12-month follow-up visit. At the 12-month visit, the patient completes the PREM questionnaire. No systematic nurse or psychological follow-up between diagnosis and the 12-month visit, unless requested by the patient. 
Visit Schedule Summary
 
  
 Visits	Day 0 (Announcement)	Day 15 (V1)	6 Months (V2)	12 Months (V3)	
   
 Informed Consent	X	-	-	-	
 
 Control Group (Usual Care)	PREM	-	-	PREM	
 
 Experimental Group (Enhanced Support)	HADS	HADS	HADS + Psychologist	HADS + PREM	
  
	Visits	Day 0 (Announcement)	Day 15 (V1)	6 Months (V2)	12 Months (V3)	Informed Consent	X	-	-	-	Control Group (Usual Care)	PREM	-	-	PREM	Experimental Group (Enhanced Support)	HADS	HADS	HADS + Psychologist	HADS + PREM
Visits	Day 0 (Announcement)	Day 15 (V1)	6 Months (V2)	12 Months (V3)																	
Informed Consent	X	-	-	-																	
Control Group (Usual Care)	PREM	-	-	PREM																	
Experimental Group (Enhanced Support)	HADS	HADS	HADS + Psychologist	HADS + PREM																	
Planned Study Timeline	
Expected study start date: September 2025
 
Participant involvement duration: 12 months
 
Visit frequency: As detailed in the visit schedule above
 
Expected inclusion period: 10 months (approximately 8 patients enrolled per month)
 
Total study duration: 24 months
																				
Source of Funding	The project is funded by the APRESO program of the GIRC.

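### As written, the early-withdrawal criteria can take randomised patients out before Month 12 and lose the PREM, the only outcome compared between arms

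*Protocol*

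**What the plan says.** The protocol summary has a row headed "Criteria for early withdrawal or study discontinuation". Its first entry is "Occurrence of other medical conditions or treatments which could interfere with the planned assessments of the study". The second is the participant's own decision to leave. The third is "A participant may also be withdrawn from the study by the investigator", with no grounds or limits given. The document does not say whether data collection continues after any of these.

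Under Evaluation Criteria and Outcome Measures, PREM satisfaction is compared between the experimental and control groups: "Measurement will be performed at 12 months". HADS change is specified for the experimental group only, and RETEX is feedback from the paramedical team.

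Under Study Procedure, the experimental arm has PREM at one point: "Visit 4 (12 months): Ophthalmology consultation; nurse consultation (HADS-3); PREM questionnaire to assess patient satisfaction". The schedule table agrees. For controls, "At the 12-month visit, the patient completes the PREM questionnaire". The table also shows a Day 0 PREM for controls, which the visit text does not mention. The Population row gives 80 patients, 40 per group.

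**The concern.** The same idea appears twice in the protocol with different consequences. As an exclusion criterion, an interfering condition or treatment acts before randomisation and leaves the comparison intact. As a withdrawal criterion it acts after randomisation. The patients then analysed at Month 12 would be those who stayed free of such events, or whose investigator did not act on them.

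The outcome exposed is the one that matters most. An experimental patient who leaves before Month 12 has no PREM value at all, and a control has at most the Day 0 value in the table. A condition or treatment arising in the year after diagnosis may well relate to how the patient experiences care, so the missing values need not be a random subset. Which patients stay in follow-up and which questionnaires are sought are protocol rules. A later analysis plan can choose how to handle missing values but cannot recover a questionnaire that was never collected.

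**Working it through.** **What the document fixes.** The sample is 40 + 40 = 80 (Population), which agrees with 10 months × about 8 patients per month (Planned Study Timeline). It states no significance level, power, effect size, SD or withdrawal rate, so there is no power figure to reproduce. Everything below except the 40 per arm is an assumption.

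**Which outcomes are exposed.**

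| Outcome | Compared between arms? | Value left if the patient leaves before Month 12 |
|---|---|---|
| PREM, experimental | Yes, at Month 12 | None |
| PREM, control | Yes, at Month 12 | At most Day 0 (table only) |
| HADS, experimental | No, single arm | Values collected before leaving; Month 12 lost |
| RETEX | No, staff feedback | Not a patient outcome |

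Only PREM bears on the randomised comparison. The HADS loss is partial and affects no between-arm contrast.

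**Precision.** One withdrawal is 1/40 = 2.5% of an arm. For a two-sample t test (two-sided 5%, 80% power, SD = 1, no correlation used), the detectable difference d solves P(|T| > t₀.₉₇₅) = 0.80. Here T is noncentral t with n₁ + n₂ − 2 degrees of freedom and noncentrality d/√(1/n₁ + 1/n₂). The 95% half-width is t₀.₉₇₅ × √(1/n₁ + 1/n₂).

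| Assumed loss | n per arm | Detectable difference (SD) | Rise | 95% half-width (SD) |
|---|---|---|---|---|
| none | 40 v 40 | 0.634 | – | 0.445 |
| 5% both | 38 v 38 | 0.651 | 2.7% | 0.457 |
| 10% both | 36 v 36 | 0.670 | 5.6% | 0.470 |
| 20% both | 32 v 32 | 0.711 | 12.2% | 0.500 |

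With loss in one arm only, the detectable difference is 0.643 (38 v 40), 0.652 (36 v 40) or 0.674 SD (32 v 40). The normal approximation (1.960 + 0.842) × √(1/n₁ + 1/n₂) gives slightly lower values: 0.626, 0.643, 0.660 and 0.700 SD for the four rows of the table.

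**Bias, as illustration.** Let p be the share of an arm lost and g the mean PREM of retained minus lost patients. The full-arm mean is (1 − p) × retained + p × lost, so retained minus full-arm mean = p × g. If g is the same in both arms, the arm difference shifts by (p_exp − p_ctrl) × g.

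| Assumed loss, exp v control | g = 0.25 SD | g = 0.5 SD | g = 1.0 SD |
|---|---|---|---|
| 10% v 5% | 0.0125 | 0.025 | 0.05 |
| 10% v 0% | 0.025 | 0.05 | 0.10 |
| equal | 0 | 0 | 0 |

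An extreme case, 20% lost in one arm only with a 1 SD gap, gives 0.20 × 1.0 = 0.20 SD. All of these lie below the 0.445 SD half-width at full sample size.

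**The case against.** The strongest reply is that this is a summary, and three short entries in a summary would not normally carry post-withdrawal procedures. A reader might infer that the protocol makes withdrawal automatic, or that it rejects recording the event. The text supports neither. It lists criteria, the investigator line is permissive, and the document is silent both on recording and on a PREM after withdrawal. What stands against the reply is that the listed consequence of an interfering event is leaving the study, and no sentence limits that to anything less.

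Exposure is also probably low. Patients with interfering conditions or treatments, and those unable to attend all visits, are excluded at entry. The patient outcomes are questionnaires. Only new events judged able to interfere within 12 months would count. That stands, and it means the 5% to 20% losses cannot be attributed to this criterion.

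A reader might go further and infer that loss will be heavier in the experimental arm, because that arm has nurse contacts at Day 15 and Month 6 while for controls there is "No systematic nurse or psychological follow-up between diagnosis and the 12-month visit, unless requested by the patient". Events could be noticed more often where patients are seen more often, so differential loss is possible. The document does not show that it occurs.

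Finally, seeking questionnaires from everyone who has not withdrawn consent would be too broad. Someone could become deprived of liberty, placed under legal protection or unable to consent after randomisation. That objection is right, and the fix allows for it.

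**Conclusion.** The point holds as a minor one that is cheap to correct. The protocol states a withdrawal rule that, applied as written, can remove randomised patients before Month 12 and lose the only between-arm outcome, with no earlier experimental-arm value to fall back on. The one certain cost is 2.5% of an arm for each patient lost. The precision losses of about 3% to 12% rest on assumed loss rates, 5% significance and 80% power, none of which the document gives. Bias cannot be computed from the document. With 10% lost in one arm, 0% or 5% in the other, and the same assumed gap of up to 1 SD in both, it would be at most 0.10 SD. The stronger conclusion, that the trial will be biased or materially underpowered by this rule, is not supported.

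**What to change.** Reword the first criterion so that an intercurrent condition or treatment is recorded with its date and does not by itself end study follow-up. State that the Month 12 PREM, and the Month 12 HADS in the experimental group, is still sought from every randomised participant. The exceptions are withdrawal of consent, or entry into a legal status in which continued participation is not permitted (the L1121-6 and L1121-8 categories in the Exclusion Criteria).

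Add to the investigator line what such a withdrawal ends, and that it does not by itself stop collection of the Month 12 questionnaires, with the same exceptions. Both changes concern data collection only; they leave the patient's care and support untouched.

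The cost is one or two sentences in the protocol and one REDCap field for the event and its date. The downside is that some Month 12 scores will reflect concurrent illness or treatment; the recorded date allows these to be identified.

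### The procedure text starts HADS at Day 15, the schedule table at Day 0, and the 15-day change in criterion 2 can be formed only under the table

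*Protocol*

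**What the plan says.** Three places in the protocol summary bear on the HADS in the experimental group.

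- **Evaluation Criteria and Outcome Measures, item 2:** "Change in HADS (Hospital Anxiety and Depression Scale) scores in the experimental group at 15 days, 6 months, and 12 months". No reference score is named.
- **Study Procedure, Experimental Group:** the announcement visit reads "Visit 1 (Diagnosis Announcement): Ophthalmologist consultation; project information; optional initial discussion with the nurse", with consent collected but no HADS listed. The Day 15 nurse consultation is "to explain the disease and procedures, and assess emotional state (HADS-1" by its numbering. Next come "Visit 3 (6 months): Nurse consultation (HADS-2); psychologist consultation offered" and, at 12 months, "nurse consultation (HADS-3); PREM questionnaire to assess patient satisfaction". That makes three HADS, the first at Day 15.
- **Visit Schedule Summary table:** the experimental row, over the columns Day 0, Day 15, 6 months and 12 months, reads "Experimental Group (Enhanced Support) HADS HADS HADS + Psychologist HADS + PREM". That makes four HADS, the first at Day 0.

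Two neighbouring entries matter for how much weight the table can carry. Its control row reads "Control Group (Usual Care) PREM - - PREM", which puts a PREM at Day 0. Criterion 1 sets the PREM measurement at 12 months, and the control procedure says only "At the 12-month visit, the patient completes the PREM questionnaire". The visit labels also differ: Visit 2 is Day 15 in the text, while V2 is 6 months in the table.

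**The concern.** A change at 15 days needs a score from before Day 15. The table provides one and the procedure text does not. Because the text numbers the Day 15 form as HADS-1, this is more than a line left out at Visit 1: under the table the Day 15 form would be the second.

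The choice also alters what the psychological-impact criterion measures. HADS-1 is taken within the first scheduled nurse consultation of the new pathway, so a Day 15 reference is not clearly a score from before support began.

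A Day 0 score can be obtained only at the announcement visit. If staff work from the procedure text it is never taken, and no analysis plan can restore it. If some patients are handled by the text and others by the table, the reference score differs between patients.

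**Working it through.** The protocol gives no computed figure to reproduce here. The check is a count of assessments, set against what criterion 2 needs.

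**Inputs**

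- Experimental group size: 40 of 80 patients (Population).
- HADS times in the procedure text: Day 15, 6 months, 12 months.
- HADS times in the table: Day 0, Day 15, 6 months, 12 months.
- Changes named in criterion 2: 15 days, 6 months, 12 months.
- Enrolment: about 8 patients per month for 10 months (Planned Study Timeline).

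**Number of forms**

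- Table: 4 × 40 = 160.
- Procedure text: 3 × 40 = 120.
- Difference: 160 − 120 = 40, all of them Day 0 scores.

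**Changes that can be formed**

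| Change in criterion 2 | Table (reference Day 0) | Procedure text (earliest score Day 15) |
|---|---|---|
| 15 days | Day 15 − Day 0 | none: no earlier score |
| 6 months | 6 months − Day 0 | 6 months − Day 15 |
| 12 months | 12 months − Day 0 | 12 months − Day 15 |
| Total | 3 of 3 | 2 of 3 |

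The 6- and 12-month changes exist under both schedules, but they are different quantities because the reference differs.

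**Rate of loss if the procedure text is followed**

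- 8 patients per month × 40/80 = 4 experimental patients per month.
- 4/40 = 10% of the Day 0 scores per month of enrolment.
- Over the inclusion period, 10 × 4 = 40, the same total as above. This assumes even enrolment and even allocation, and shows only how quickly a late correction loses value.

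**Does the table settle it?** Not by itself. Both questionnaire entries in its Day 0 column (HADS for the experimental group, PREM for controls) are missing from the procedure text, 2 of 2. The table therefore departs from the text on a second instrument too.

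**Possible readings of criterion 2**

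- (a) Change from a Day 0 score. This fits the idea of a change at 15 days and fits the table, but the procedure text does not collect that score.
- (b) Course of scores over the three listed times, with Day 15 as the starting point. This fits the procedure text and objective 2, but then there is no 15-day change and the table's Day 0 HADS has no stated use.

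Neither reading is consistent with all three places.

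**The case against.** The strongest reply is that reading (b) is the natural one. The three times in criterion 2 are exactly those of HADS-1 to HADS-3, and objective 2 only sets out to collect data on patients' experience after diagnosis. On that view no 15-day change was meant, nothing is lost, and the table is simply the outlier. This reading is tenable, so the loss of the 15-day change must be stated as conditional on the procedure text being followed and a change from Day 0 being intended. It does not remove the contradiction: the table still orders a form that the text omits, and criterion 2 still lists a change at the time that would be its own starting point.

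A second reply is that the reference for a change score is often fixed in a statistical analysis plan, which is not shown. That is fair for the definition alone, and the missing reference would carry little weight by itself. Whether a form is handed out at the announcement visit, however, is a matter of data collection that only the protocol can settle.

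Third, the Planned Study Timeline refers to the visit schedule for visit frequency, which gives the schedule some standing. It concerns visits, and text and table agree on the four time points, so it does not decide which questionnaires are completed.

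Finally, this is a descriptive, single-arm criterion in a single-centre pilot study, and mixed handling between patients is a possibility rather than a prediction. Both points stand and limit the weight of the finding.

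**Conclusion.** The concern holds. The procedure text and the schedule table cannot both be right about a Day 0 HADS, and nothing in the document reconciles them. At stake are 40 Day 0 scores (160 forms against 120) and one of the three changes named in criterion 2, together with the meaning of the other two. The loss of the 15-day change is conditional on the procedure text being the version followed. It would be irreversible for each patient already past the announcement visit.

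The scope is limited to one of three evaluation criteria, reported in the experimental group only. The HADS discrepancy leaves the randomized 12-month PREM comparison untouched. The documents give no HADS values, so no size of score difference is claimed.

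**What to change.** Reconcile the procedure text, the table and criterion 2 before enrolment, or as soon as possible if it has begun. Two coherent solutions are open to the sponsor.

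1. **Keep the Day 0 HADS (preferred, because it preserves all three changes).** Add it to Visit 1 in the procedure text, after consent, and word criterion 2 as change from the Day 0 HADS at Day 15, 6 months and 12 months. The cost is one short questionnaire for each of 40 patients compared with the procedure text, and nothing beyond what the table already schedules. Like the table, it presupposes that allocation is known at the announcement visit. The document does not state this, so it needs to be confirmed.
2. **Drop the Day 0 HADS.** Delete it from the table and restate criterion 2 as change from the Day 15 HADS at 6 and 12 months, with no 15-day change. The cost is wording only, but the 15-day change is given up and the reference falls within the first scheduled nurse consultation.

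In either case, use one numbering for HADS forms and visits in text and table, and settle in the same revision whether controls complete a PREM at Day 0. The renumbering is wording only.

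### The Month 12 PREM, the only patient outcome compared between arms, is tied to a visit that the two arms may miss at different rates

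*Protocol*

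**What the plan says.** Evaluation Criteria and Outcome Measures lists PREM first and compares it between the experimental and control groups. On timing it says "Measurement will be performed at 12 months". HADS change is described for the experimental group alone, and RETEX is feedback from staff. The schedule table also shows a PREM at Day 0, but for controls only, so it offers no second comparison.

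The Study Procedure attaches the Month 12 PREM to a visit in each arm:

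- Control: "At the 12-month visit, the patient completes the PREM questionnaire".
- Experimental, Visit 4: "Ophthalmology consultation; nurse consultation (HADS-3); PREM questionnaire to assess patient satisfaction".

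No postal, online or telephone route is given for PREM. A telephone option appears only for the experimental Day 15 contact: "Nurse consultation (in-person or by phone, ~1 hour". The Inclusion Criteria require a number ("Has a valid telephone number") but do not link it to PREM.

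Between diagnosis and Month 12 the experimental arm has nurse contacts at Day 15 and Month 6. For controls the text says "No systematic nurse or psychological follow-up between diagnosis and the 12-month visit, unless requested by the patient". The Study Justification says that "the long medical journey and lack of clear guidance increase anxiety, sometimes leading to a break in follow-up care".

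**The concern.** The difference in contact is the intervention and is not a fault. The difficulty is that the outcome is observed only if the patient returns. The protocol's own rationale implies that returning may depend on the guidance that one arm receives and the other does not. If so, the patients with a PREM score may be selected differently in the two arms, and the comparison of those scores would no longer be protected by randomisation.

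An analysis plan can model missing scores, but it cannot collect them afterwards. The route of collection is therefore a matter for the Study Procedure and not for an analysis plan that is not shown here.

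**Working it through.** **Figures in the protocol.** 40 + 40 = 80 patients, and 8 per month x 10 months = 80, so the sample and accrual figures agree. No attrition rate, PREM standard deviation or target difference is stated. Every rate and gap below is an assumption.

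**Formula.** Let l be the share without a PREM in an arm, and g the amount in SD by which non-returners are less satisfied than returners. The mean among returners exceeds the full-arm mean by g x l. With the same g in both arms:

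bias in (experimental - control) = g x (l_E - l_C)

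A negative value means the benefit is understated.

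| Assumed loss, E v C | g = 0.5 | g = 1.0 |
|---|---|---|
| 10% v 20% | 0.5 x (0.10 - 0.20) = -0.05 | -0.10 |
| 10% v 30% | -0.10 | 1.0 x (0.10 - 0.30) = -0.20 |
| 10% v 10% | 0 | 0 |
| 20% v 10% | +0.05 | +0.10 |

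If loss is unrelated to satisfaction (g = 0), the bias is zero at any rate of loss.

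**Against the precision available.** The standard error in SD units is sqrt(1/n_E + 1/n_C).

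- 40 v 40: 0.224.
- 36 v 32 (10% v 20% loss): 0.243, so 0.05/0.243 = 0.21 of a standard error.
- 36 v 28 (10% v 30% loss): 0.252, so 0.20/0.252 = 0.79 of a standard error.

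For scale, the difference detectable with 80% power at two-sided 5% is (1.96 + 0.84) x SE, which is 0.63 SD for 40 v 40 and 0.71 SD for 36 v 28.

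**What a remote route would do.** If some non-attenders are reached, l in the formula is replaced by l minus the share of reached patients among all those observed.

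- *A random half reached in each arm.* 10% v 20%, g = 0.5: 0.5 x [(0.10 - 2/38) - (0.20 - 4/36)] = -0.02. 10% v 30%, g = 1: (0.10 - 2/38) - (0.30 - 6/34) = -0.08.
- *Half reached, but only the more satisfied half (half the gap).* The same two cases give -0.04 and -0.14.
- *Unequal reach, 75% E v 25% C.* 10% v 20%, g = 0.5: 0.5 x [(0.10 - 3/39) - (0.20 - 2/34)] = -0.06. 10% v 30%, g = 1: (0.10 - 3/39) - (0.30 - 3/31) = -0.18. With equal 15% loss, where there was no bias, (0.15 - 4.5/38.5) - (0.15 - 1.5/35.5) = -0.07 for g = 1 and -0.04 for g = 0.5.

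The route helps when reach is similar in the two arms. When reach is unequal it can fail to help, or can create a bias.

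**The case against.** Completing a questionnaire at a scheduled visit is ordinary practice, and the rule is the same in both arms. The document is headed as a summary, and reminders and missed-visit procedures are details that a summary often omits. A reader might infer that patients who miss Month 12 will not be contacted. The text does not say so, and the outcome definition fixes only a time. That part of the objection stands: the finding is about what is stated, and the full protocol may say more.

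A reader might also infer that the comparison is biased against the intervention, or that the trial is invalid. Neither is supported. The rationale says only that a break sometimes occurs, speaks of patients in general and gives no rate. Three features lower the risk: people unable to attend every visit are excluded at entry, controls may ask for support, and the Month 12 visit is itself part of the control pathway ("Usual care: Diagnosis consultation followed by a 12-month follow-up visit"). The extra experimental visits could even raise loss in that arm. These points lessen the risk without removing it, since an entry criterion cannot prevent disengagement during the following year.

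The size is also modest. The upper figure needs three times the loss in controls together with a full 1 SD gap. Greater control loss would understate benefit and so would not produce a false claim of it: at -0.20 SD with SE 0.252, the one-sided chance of a false benefit falls from 2.5% to about 0.3%. Understating benefit still matters in a pilot meant to inform wider use.

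**Conclusion.** The point holds as a conditional one. As written, whether the only between-arm patient outcome is observed depends on attending Month 12, and the intervention may affect attendance. The documents establish neither the direction nor the size of any bias. The 0.05-0.20 SD (0.2-0.8 of a standard error) rests wholly on assumed losses of 10% v 20-30%, an assumed 0.5-1.0 SD gap and an equal gap in both arms; other equally admissible assumptions give zero or the opposite sign. This is an inexpensive improvement of optional strength. It has some value even if loss is equal, because it recovers scores that cannot be obtained later.

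**What to change.** Amend the Study Procedure as follows.

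- Seek the Month 12 PREM from every randomised patient who has not withdrawn consent, whether or not they attend.
- Use one remote route in both arms: a self-completed online link, or telephone using the number already required. Make the same number of attempts in each arm.
- State a window around Month 12 that fits the timeline and the stated 12-month participation. Inclusion plus participation takes 10 + 12 = 22 of 24 months. A window closing, for example, 4 weeks after Month 12 would end at about month 22.9 for the last patient, leaving about one month for cleaning and analysis.
- Record the mode of completion and report PREM completion by arm.
- Reconcile this with the criteria for early withdrawal by stating whether patients withdrawn by the investigator are still asked for the PREM.

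No additional staff are required. If calls are made, they should preferably not be made by the nurses who delivered the intervention.

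Under the assumed losses the cost is 4 + 8 = 12 to 4 + 12 = 16 extra patients to contact. The downsides are a possible mode effect and unequal reach despite equal effort. With half reached in each arm, a mode effect favouring remote answers would have to be as large as the satisfaction gap itself to cancel the gain: for 10% v 30% loss it adds m x (2/38 - 6/34) = -0.124m, against a gain of 0.124g.
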